## **6.2 Data collection and enrolment**

Visit specific assessments and the order in which they should be performed are described in [Table 3](#) and in [Appendix E](#) (Visit to Visit Guide).

During the Screening Visit a separate Screening Informed Consent will be obtained before the screening procedure is performed, which consists of taking a blood sample for determination of HbA1c. A Screening number (S code) will be created for all patients by the investigator. This S-code will identify screening laboratory results together with date of birth and gender.

In addition to what is specified in [Table 3](#) for enrolment, the following demographic data will be collected and recorded in the appropriate sections of the eCRF:

- Date of birth, sex, race and ethnicity
- Information about smoking, alcohol, medical history, specific disease history and family history on coronary heart disease

### **6.2.1 Follow-up procedures**

A Follow-up Visit (Visit 18) will be performed 18-24 days (3 weeks  $\pm$ 3 days) after the End of Treatment Visit (Visit 17), see [Table 3](#) for further details.

Patients who prematurely discontinue double blind study drug treatment due to general or study specific discontinuation criteria will have a follow up visit 3 weeks after End of Treatment Visit (Visit 17).

### **6.3 Efficacy**

### 6.3.1 Efficacy laboratory variables

**Table 8 Efficacy laboratory variables**

Visit	S	1	2	3	4	5	6	7	8	9	10	11	12	13	14	15	16	17 EoT	18	R
Study Week	-7	-5	-4	-2	0	1	4	8	16	24	28	36	44	52	65	78	91	104	107	
HbA1c	X	X	X	X	X	X	X	X	X	X	X	X	X	X	X	X	X	X	X	X
FPG a		X	X	X	X	X	X	X	X	X	X	X	X	X	X	X	X	X	X	X
Insulin, pro-insulin a					X					X				X		X		X		X
HOMA-2, HOMA-IR					X					X				X		X		X		X
Total cholesterol a		X			X					X				X		X		X		X
LDL-C a		X			X					X				X		X		X		X
HDL-C a		X			X					X				X		X		X		X
TG a		X			X					X				X		X		X		X
FFA a, b					X					X				X		X		X		X
hs-CRP c					X					X				X		X		X		X

a fasting

b free fatty acids;

c high sensitivity C-Reactive Protein.

The laboratory parameters that will be measured to assess efficacy are displayed in [Table 8](#) by visit. The results from baseline and onwards will not be reported to the investigator, except for TC, HDL-C, LDL-C and TG which will be reported.

### **6.3.2 HbA1c**

HbA1c will be analysed by a central laboratory according to the procedures described in the Laboratory Manual which will be distributed to each study site. HbA1c will be blinded during the treatment period.

### **6.3.3 Body weight**

The patient's weight will be recorded in kilogram (kg) to one decimal place, on a fasting stomach with light clothing and without shoes. All readings should be recorded as accurately as possible and the same scales should be used for all assessments for a given patient.

### **6.3.4 Blood pressure**

Systolic and diastolic blood pressure are both an efficacy and safety variable in this study, measurement of BP is described in Section 6.4.8.

### **6.3.5 HOMA-2, HOMA-IR**

HOMA-2 and HOMA-IR are methods for assessing  $\beta$ -cell function and insulin resistance from glucose and insulin or C-peptide concentrations. These will be calculated by AstraZeneca.

## **6.4 Safety**

The Principal Investigator is responsible for ensuring that all staff involved in the study is familiar with the content of this section.

### **6.4.1 Definition of adverse events**

An adverse event is the development of an undesirable medical condition or the deterioration of a pre-existing medical condition following or during exposure to a pharmaceutical product, whether or not considered causally related to the product. An undesirable medical condition can be symptoms (eg, nausea, chest pain), signs (eg, tachycardia, enlarged liver) or the abnormal results of an investigation (eg, laboratory findings, electrocardiogram). In clinical studies, an AE can include an undesirable medical condition occurring at any time, including run-in or washout periods, even if no study treatment has been administered.

The term AE is used to include both serious and non-serious AEs.

### **6.4.2 Definitions of serious adverse event**

A serious adverse event is an AE occurring during any study phase (ie, run-in, treatment, washout, follow-up), that fulfils one or more of the following criteria:

- Results in death
- Is immediately life-threatening
- Requires in-patient hospitalisation or prolongation of existing hospitalisation

- Results in persistent or significant disability or incapacity
- Is a congenital abnormality or birth defect
- Is an important medical event that may jeopardise the patient or may require medical intervention to prevent one of the outcomes listed above.
- Cancer
- Drug dependency/abuse

An overdose (defined as the accidental or intentional ingestion of any dose of the investigational product that is considered both excessive and medically important – see Section 13.2) should be reported as an SAE using the most relevant SAE criteria, as judged by the Investigator.

For further guidance on the definition of a SAE, see [Appendix B](#) to the Clinical Study Protocol.

### **6.4.3 Recording of adverse events**

#### **Time period for collection of adverse events**

Adverse Events will be collected from the start of the lead-in period (Visit 2) throughout the treatment period and including the follow-up period (Visit 18).

SAEs will be recorded from the time of informed consent until the end of the study (Visit 18).

#### **Follow-up of unresolved adverse events**

Any AEs that are unresolved at the patient's last visit in the study are followed up by the investigator for as long as medically indicated, but without further recording in the eCRF. AstraZeneca retains the right to request additional information for any patient with ongoing AE(s)/SAE(s) at the end of the study, if judged necessary. The requirement to follow-up is not intended to delay database lock or production of the clinical study report. Both these activities should proceed as planned with ongoing AEs if necessary.

Any follow-up of ongoing SAEs after database lock will be reported to AstraZeneca, who will notify the appropriate Bristol-Myers Squibb Pharmacovigilance contact.

#### **Variables**

The following variables will be collected for each AE;

- AE (verbatim)
- the date when the AE started and stopped
- maximum intensity

- whether the AE is serious or not
- investigator causality rating against the Investigational Product (yes or no)
- action taken with regard to investigational product
- outcome.

In addition, the following variables will be collected for SAEs:

- Date AE met criteria for serious AE
- Date Investigator became aware of serious AE
- AE is serious due to
- Date of hospitalisation
- Date of discharge
- Probable cause of death
- Date of death
- Autopsy performed
- Causality assessment in relation to Study procedure(s)
- Causality assessment in relation to Other medication
- Description of AE.

Maximum intensity will be graded according to the following rating scale:

1. mild (awareness of sign or symptom, but easily tolerated)
2. moderate (discomfort sufficient to cause interference with normal activities)
3. severe (incapacitating, with inability to perform normal activities)
4. very severe (debilitating, significantly incapacitates patient despite symptomatic therapy).

It is important to distinguish between serious and severe AEs. Severity is a measure of intensity whereas seriousness is defined by the criteria in Section 6.4.2. An AE of severe intensity need not necessarily be considered serious. For example, nausea that persists for several hours may be considered severe nausea, but not a SAE. On the other hand, a stroke

that results in only a limited degree of disability may be considered a mild stroke but would be a SAE.

### **Causality collection**

The Investigator will assess causal relationship between Investigational Product and each Adverse Event, and answer 'yes' or 'no' to the question 'Do you consider that there is a reasonable possibility that the event may have been caused by the investigational product?'

For SAEs causal relationship will also be assessed for other medication and study procedures. Note that for SAEs that could be associated with any study procedure the causal relationship is implied as 'yes'.

A guide to the interpretation of the causality question is found in [Appendix B](#) to the Clinical Study Protocol.

### **Adverse Events based on signs and symptoms**

All AEs spontaneously reported by the patient or reported in response to the open question from the study personnel: 'Have **you** had any health problems since the previous visit/you were last asked?', or revealed by observation will be collected and recorded in the eCRF. When collecting AEs, the recording of diagnoses is preferred (when possible) to recording a list of signs and symptoms. However, if a diagnosis is known and there are other signs or symptoms that are not generally part of the diagnosis, the diagnosis and each sign or symptom will be recorded separately.

### **Adverse Events based on examinations and tests**

Deterioration as compared to baseline in protocol-mandated laboratory values, vital signs and other safety variables will only be reported as AEs if they are clinically significant, fulfil any of the SAE criteria or are the reason for discontinuation of treatment with the investigational product, or require the patient to receive specific corrective therapy.

If deterioration in a laboratory value/vital sign is associated with clinical signs and symptoms, the sign/symptom will be reported as an AE and the associated laboratory result/vital sign will be considered as additional information. Any new or aggravated clinically relevant abnormal medical finding at a physical examination as compared with the baseline assessment will be reported as an AE.

Wherever possible the reporting investigator uses the clinical, rather than the laboratory term (eg, anaemia versus low haemoglobin value).

### **Hypoglycaemic events**

A separate section in the eCRF will be used to document all reported episodes of hypoglycaemia. Hypoglycaemic episodes or discontinuation due to hypoglycaemia should not be reported on the AE eCRF page unless the event fulfils protocol criteria for a Serious Adverse Event (see Section [6.4.2](#)). In this case, an SAE must be reported in addition to the

hypoglycaemia eCRF pages for hypoglycaemia. The Investigator is responsible for questioning the patient about all symptoms reported in the diary and for determining if they meet the clinical definition of hypoglycaemia. Only symptoms and/or blood glucose values deemed by the Investigator to meet the definition of hypoglycaemia should be reported on the hypoglycaemia eCRF pages (see Section 6.4.9.1).

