## LIST OF ABBREVIATIONS AND DEFINITION OF TERMS

The following abbreviations and special terms are used in this study Clinical Study Protocol.

Abbreviation or special term	Explanation
AE	Adverse event (see definition in Section 6.4.1)
ANCOVA	Analysis of covariance
ALT	Alanine aminotransferase
AST	Aspartate aminotransferase
BMI	Body Mass Index
CEC	Clinical Event Committee
CK	Creatine kinase
CRF	Case Report Form (electronic/paper)
CSA	Clinical Study Agreement
CSR	Clinical Study Report
CTCAE	Common Terminology Criteria for Adverse Event
DAE	Discontinuation of Investigational Product due to Adverse Event
CV	Cardiovascular
DBP	Diastolic blood pressure
DNA	Deoxyribonucleic acid
DPP-4	Dipeptidyl-peptidase-4
ECG	Electrocardiogram
EC	Ethics Committee, synonymous to Institutional Review Board (IRB) and Independent Ethics Committee (IEC)
eCRF	Electronic Case Report Form
eGFR	Estimated glomerular filtration rate
EMA	European Medicines Agency
EQ-5D	EuroQol EQ-5D questionnaire
FDA	Food and Drug Administration
FPG	Fasting plasma glucose
GCP	Good Clinical Practice
GTI	Genital tract infection
HbA1c	Glycosylated haemoglobin A1c
HRQL	Health-related quality of life

---

Abbreviation or special term	Explanation
ICH	International Conference on Harmonisation
International Co-ordinating investigator	If a study is conducted in several countries the International Co-ordinating Investigator is the Investigator co-ordinating the investigators and/or activities internationally.
IP	Investigational Product
IVRS	Interactive Voice Response System
IWRS	Interactive Web Response System
LIMS	Laboratory Information Management System
LLOQ	Lower Limit of Quantification
LOCF	Last observation carried forward
LSLV	Last Subject Last Visit
MI	Myocardial infarction
MODY	Maturity-onset diabetes of young
OAD	Oral anti-diabetic medication
OAE	Other Significant Adverse Event (see definition in Section 11.2.1 )
PAD	Peripheral Artery Disease
PGx	Pharmacogenetic(s)
PI	Principal Investigator
PPG	Postprandial glucose
PRO	Patient reported outcomes
QD	Daily
SAE	Serious adverse event (see definition in Section 6.4.2 ).
SBP	Systolic blood pressure
SAP	Statistical Analysis Plan
T2DM	Type 2 diabetes mellitus
TB	Total bilirubin
ULN	Upper limit of normal
UTI	Urinary tract infection
WBDC	Web Based Data Capture

---

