### **General discontinuation criteria:**

1. Patient decision. The patient is at any time free to discontinue treatment, without prejudice to further treatment
2. Adverse Event, ie, any clinical AE, laboratory abnormality or intercurrent illness which, in the opinion of the investigator, indicates that continued participation in the study is not in the best interest of the patient
3. Severe non-compliance to study protocol as judged by the investigator and/or AstraZeneca
4. Risk to patients as judged by the investigator and /or AstraZeneca
5. Incorrectly enrolled patients (see Section 5.3)
6. Patient lost to follow-up (see Section 5.9)
7. Withdrawal of informed consent to the use of biological samples collected as an integral part of the study, (see Section 7.5)

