### **Development of any study specific criteria for discontinuation:**

8. Treatment with glucocorticoids equivalent to oral prednisolone >10 mg/day (two temporary periods of higher daily doses for no longer than 7 days each are allowed)
9. Major and/or frequent hypoglycaemic events, defined as  $\geq 1$  major event or recurring minor events (See 6.4.9.1 for definition of minor and major). This definition should be applied after possible contributing factors (eg, excessive physical activity) have been excluded by the investigator

10. Pregnancy confirmed by a positive pregnancy test or otherwise verified
11. Change in kidney function (Please see [Appendix K](#) for further guidance):
  - For all patients treated with metformin: calculated creatinine-clearance <60 mL/min or an increase in serum creatinine of  $\geq 44 \mu\text{mol/L}$  ( $\geq 0.5 \text{ mg/dL}$ ) above the baseline value confirmed by a repeated measurement within one week.
  - For patients not treated with metformin: a) calculated creatinine clearance <60 ml/min or b) in subjects with baseline creatinine  $\geq 123 \mu\text{mol/L}$  ( $\geq 1.4 \text{ mg/dL}$ ) an absolute increase in serum creatinine of  $\geq 88 \mu\text{mol/L}$  ( $\geq 1.0 \text{ mg/dL}$ ), or c) in subjects with baseline creatinine <123  $\mu\text{mol/L}$  (<1.4 mg/dL) an absolute increase in serum creatinine of  $\geq 44 \mu\text{mol/L}$  ( $\geq 0.5 \text{ mg/dL}$ ).
12. CK >10x ULN confirmed at a repeated measurement preferably within 24 hours, but not exceeding 72 hours, see Section [5.8.1](#)
13. Patients with a central laboratory ALT and/or AST >3x ULN will be scheduled for a follow-up visit within 3 days following the receipt of the result. See [Appendix J](#) for further guidance. Patients should be discontinued from treatment if the initial **and** repeated laboratory tests meet any of the following criteria:
  - ALT and/or AST are >3x ULN **and** TB>1.5x ULN
  - ALT and/or AST are >5x ULN for  $\geq 14$  consecutive days, at any time after initial confirmatory results
  - ALT and/or AST are >8x ULN.
14. Serum Sodium  $\leq 125 \text{ mmol/L}$  with or without symptoms; see [Appendix I](#) for further guidance

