## **11.2 Calculation or derivation of safety variable(s)**

### **11.2.1 Other significant adverse events (OAE)**

During the evaluation of the AE data, an AstraZeneca medically qualified expert will review the list of AEs that were not reported as SAEs and DAEs. Based on the expert's judgement, significant adverse events of particular clinical importance may, after consultation with the Global Patient Safety Physician, be considered OAEs and reported as such in the Clinical Study Report. A similar review of laboratory/vital signs/ECG data will be performed for identification of OAEs.

Examples of these are marked haematological and other laboratory abnormalities, and certain events that lead to intervention (other than those already classified as serious), dose reduction or significant additional treatment.

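### Stops of study drug for non-serious hypoglycaemia are kept off the AE page, so they fall outside the count of discontinuations due to adverse events, although hypoglycaemia is a protocol stopping criterion

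*Supplement*

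**What the plan says.** Four parts of the protocol bear on this.

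- **Recording rule.** Section 6.4.3, under hypoglycaemic events, sends the data to their own form: "A separate section in the eCRF will be used to document all reported episodes of hypoglycaemia". It then bars both the episodes and any resulting stop from the AE page: "discontinuation due to hypoglycaemia should not be reported on the AE eCRF page unless the event fulfils protocol criteria for a Serious Adverse Event".
- **Stopping criteria.** Section 5.8 lists as item 2 the general reason "Adverse Event, ie, any clinical AE, laboratory abnormality or intercurrent illness which" the investigator judges incompatible with continued participation. Separately, item 9 begins "Major and/or frequent hypoglycaemic events, defined as" and sets the threshold at one or more "major event or recurring minor events (See 6.4.9.1 for definition of minor and major").
- **DAE category.** The abbreviation list expands DAE as "Discontinuation of Investigational Product due to Adverse Event". Section 11.2.1 describes an expert who "will review the list of AEs that were not reported as SAEs and DAEs", which treats SAEs and DAEs as subsets of the AE list.
- **Rule for other findings.** Elsewhere in Section 6.4.3, deteriorations in laboratory values, vital signs and other safety variables become AEs if, among other conditions, they "are the reason for discontinuation of treatment with the investigational product, or require the patient to receive specific corrective therapy".

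**The concern.** A count of discontinuations due to adverse events is a basic tolerability summary, and safety and tolerability are stated objectives for the 24-week period and both extensions. A reader would expect that count to cover every patient taken off drug because of a harm. Here one harm has its own numbered stopping criterion, and the recording rule removes it from the records that define the category. Background therapy may include insulin or a sulfonylurea, so hypoglycaemia is a foreseeable reason for stopping. If such stops differ between arms, the DAE comparison is distorted in favour of whichever arm has more of them, and nothing in the table would show it.

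**Working it through.** The protocol states no figure for this point, so there is nothing to recompute. The check is to follow one patient who stops under item 9 after a non-serious event through the protocol's data flow.

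1. **Trigger.** The patient has a major event not classed as serious, or recurring minor events. Section 5.8, item 9, applies, and study drug is stopped.
2. **AE page.** Section 6.4.3 bars the episode and the stop. No AE record is created.
3. **Link between event and study drug.** The variables collected for each AE (Section 6.4.3) include the action taken with investigational product. The items collected for each hypoglycaemic event (Section 6.4.9.1) cover timing, symptoms, contributing factors, glucose value, treatment, recovery, last drug intake and last meal. None records what was done with study drug.
4. **DAE.** By its definition, and by the way Section 11.2.1 uses it, a DAE requires an AE. With no AE record, the patient is not a DAE. No section adds the patient back.
5. **Hypoglycaemia summary.** The one tabulation named, in Section 11.2.2, counts patients with at least one episode between baseline and week 24. It does not count stops.

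Set beside the other stopping criteria, the treatment of hypoglycaemia is the exception:

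| Reason for stopping | AE called for when study drug is stopped? | Where |
|---|---|---|
| Deterioration in laboratory values, vital signs, other safety variables | Yes | 6.4.3, examinations and tests |
| Confirmed creatine kinase elevation | Yes, explicitly | 5.8.1 |
| Decreased renal function | Yes, explicitly | Appendix K |
| Non-serious hypoglycaemia | No, explicitly barred | 6.4.3, hypoglycaemic events |

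Section 6.4.9.1 adds an inversion. Symptoms with a glucose value at or above 63 mg/dL are recorded as an adverse event, unless the physician doubts the reading. A stop for those symptoms can therefore become a DAE. A stop for confirmed hypoglycaemia below that value cannot, unless the event is serious.

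**The case against.** The best reply is that separate capture is deliberate and loses little. All reported episodes go into a dedicated eCRF section, hypoglycaemic events are a named safety variable, and Section 12.2.3 presents safety data by arm and by age stratum. Section 5.8.1 says a patient who decides to stop is always asked why. Events meeting SAE criteria are still reported as SAEs. No DAE table is specified in the protocol, and the SAP, which is not shown, could define one that includes these stops. The specific hypoglycaemia rule can also be read as a carve-out from the general rule for tests, not a contradiction of it.

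Much of this stands, and it limits the point. A reader might infer that hypoglycaemia data are lost, or that these patients can appear in no AE, DAE or OAE output. The documents do not support either. The episodes are kept and analysed, and the OAE review in Section 11.2.1 also covers laboratory, vital-sign and ECG data, so it is not confined to AE-page records.

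A reader might also put a size and direction on the undercount. Suppose 1 to 2% of the 470 dapagliflozin patients (940/2) stop for this reason, which is 470 × 0.01 = 4.7 to 470 × 0.02 = 9.4 patients, and suppose a 5% DAE rate, 470 × 0.05 = 23.5. The shortfall is 4.7/23.5 = 20% to 9.4/23.5 = 40% if 23.5 is the complete count. It is 4.7/28.2 = 17% to 9.4/32.9 = 29% if 23.5 is the count with these stops missing. None of those rates is in the documents.

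Nor is the direction established. Section 5.6.2.3 says to keep patients on study drug and adjust other medication, item 9 applies only after contributing factors are excluded, and background insulin is cut by 25% in both arms at randomisation. Such stops may be few.

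What the reply does not remove is the instruction itself. The protocol does not merely leave the routing open: it tells sites not to enter these stops as AEs, while other stopping rules tell them the opposite, and it gives no reason for the difference.

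**Conclusion.** The point holds as an inconsistency in recording and reporting. Following the protocol as written, stops for recurring minor hypoglycaemia, or for major hypoglycaemia not classed as serious, create no AE record and are not DAEs, and the named hypoglycaemia tabulation does not count them either. This conclusion rests on the protocol's own definition of a DAE as a stop due to an AE, and on no unseen document adding these patients back. The size and direction of the undercount cannot be derived. No primary or key secondary endpoint is affected, and safety is summarised descriptively. The matter is still worth correcting, because the tolerability comparison would otherwise silently omit one of the protocol's own stopping criteria.

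**What to change.** Either of two changes would do. Both concern recording and reporting only, and neither alters when study drug is stopped.

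- **In Section 6.4.3:** reconcile the hypoglycaemia paragraph with the rule for examinations and tests, Section 5.8.1 and Appendix K. State that hypoglycaemia is kept off the AE page unless it is serious or is the reason for permanently stopping study drug. Deleting only the words about discontinuation would not be enough, because the bar on episodes would remain.
- **In the analysis:** derive hypoglycaemia stops from the recorded reason for discontinuation, and present DAEs by arm with and without them. This needs the eCRF to hold the reason in a form that identifies item 9.

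The cost is one sentence or one derivation rule, using information that Section 5.8.1 already asks for. The downside is that the reported DAE rate may become slightly less favourable.
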